Death should be considered an outcome and not a distinct event. The event or condition that caused or contributed to the fatal outcome should be recorded as the single medical concept on the AE eCRF. Generally, only 1 such event should be reported. The term "sudden death" should be used only for the occurrence of an abrupt and unexpected death because of presumed cardiac causes in a subject with or without pre-existing heart disease within 1 hour after the onset of acute symptoms or, in the case of an unwitnessed death, within 24 hours after the subject was last seen alive and stable. If the cause of death is unknown and cannot be ascertained at the time of reporting, "unexplained death" should be recorded on the AE eCRF. If the cause of death later becomes available (e.g., after autopsy), "unexplained death" should be replaced by the established cause of death.

Lack of Efficacy or Worsening of Disease

Events that are clearly consistent with the expected pattern of progression of the underlying disease, including transformation to a more aggressive histology, are also considered an expected outcome for this study and will NOT be recorded as AEs. These data will be captured as efficacy assessment data only. If there is any uncertainty as to whether an event is due to disease progression, the event should be reported as an AE.

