6.4 Toxicity Management

Venetoclax: Venetoclax could lead to suppression of lymphocytes. In addition, clinically significant neutropenia may also be observed. Both lymphopenia and neutropenia could increase the risk for infections, including opportunistic infections. Venetoclax treatment can also lead to TLS. Subjects will be managed based on their TLS risk factors as detailed below.

Pomalidomide: Pomalidomide could lead to neutropenia, anemia, and thrombocytopenia. Among the nonhematologic toxicities, venous and arterial thromboembolism, hepatotoxicity, hypersensitivity reactions, dizziness and confusional state, and neuropathy have been reported with pomalidomide.

Dexamethasone: Dose modifications or discontinuation may be necessary for gastrointestinal events, acute pancreatitis, neurologic disorders or muscle weakness, and edema or hyperglycemia.

Subjects will be monitored for these events throughout the study and treatment may be discontinued or adjusted as appropriate. Dose modifications and treatment guidelines for drug-related toxicities (venetoclax, pomalidomide, or dexamethasone) are provided in [Appendix I](#). If an investigator considers it necessary, subjects who interrupt study therapy for longer than 28 days may be discontinued from further study therapy.

Prophylaxis and Management of Tumor Lysis Syndrome

Venetoclax and pomalidomide can cause rapid reduction in tumor and thus poses a risk for TLS. Changes in electrolytes consistent with TLS that require prompt management can occur as early as 6 to 8 hours following the first dose of venetoclax ([Appendix H](#)). Definitions of laboratory TLS and clinical TLS are provided in the [Appendix G](#) (Howard grading classification).

There is a potential for TLS in subjects affected by hematologic malignancies. Depending on the specific tumor type, risk factors may include one or more of the following: bulky disease or high tumor burden, elevated pretreatment lactate dehydrogenase levels, elevated leukocyte count, renal insufficiency, and dehydration.

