Progressive Disease: Two consecutive assessments for confirmation of PD made at any time before the start of new therapy are required per IMWG criteria ([Appendix F](#)). The second assessment may be taken immediately if PD is suspected. If PD is suspected by rising serum or urine M-protein (or FLC in subjects without measurable disease), 2 consecutive assessments from central laboratory readings should be obtained.

If PD is suspected by clinical symptoms, a plasmacytoma evaluation and/or skeletal survey should be obtained, as clinically indicated, and compared with baseline assessments to determine whether a new bone lesion or plasmacytoma has developed or an existing lesion or plasmacytoma has worsened. Serum and urine protein electrophoresis are also required.

The following assessments are not sufficient to determine PD:

- Rising serum FLC if disease is measurable in the serum, urine, or both.
- Serum FLC can be used to determine PD according to the IMWG criteria only for subjects without measurable serum and urine M-protein.
- Clinical relapse based on indicators that are not part of the IMWG criteria for PD (e.g., decrease in hemoglobin, hypercalcemia, increase in serum creatinine, hyperviscosity), and relapse from clinical relapse categories should not be considered PD.

- General worsening of the subject's condition. If a subject's condition has deteriorated to a point that remaining on protocol therapy is not an option, every effort should be made to document PD by at least one of the following assessments prior to the initiation of new therapy: serum protein electrophoresis, urine protein electrophoresis, bone marrow biopsy, plasmacytoma evaluation, or skeletal survey.

Investigators are requested not to discontinue subjects from treatment for presumed lack of response after only 1 cycle of study treatment.

Clinical Relapse: Clinical relapse is defined per IMWG criteria ([Appendix F](#)) and cannot be used to determine PD.

Evaluation of Disease

IMWG assessments will be reviewed by the investigator per the IMWG criteria ([Appendix F](#)). If the investigator confirms that the subject meets the criteria for PD by 2 consecutive assessments, the subject will be deemed as having met an event of disease progression. For the purposes of this study, the date of progression will be the date on which the IMWG assessments were obtained.

Biomarker Sampling

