Stable disease ^e	
 • Not meeting criteria for CR, VGPR, PR, MR or progressive disease
Progressive disease	
 • Any one or more of the following criteria: 
 • Increase of 25% from lowest confirmed response value in one or more of the following criteria: 
 • Serum M-protein (absolute increase must be ≥ 0.5 g/dL); • Serum M-protein increase ≥ 1 g/dL, if the lowest M-component was ≥ 5 g/dL; • Urine M-protein (absolute increase must be ≥ 200 mg/24 hr); • In patients without measurable serum and urine M-protein levels, the difference between involved and uninvolved FLC levels (absolute increase must be > 10 mg/dL); • In patients without measurable serum and urine M-protein levels and without measurable involved FLC levels, bone marrow plasma-cell percentage irrespective of baseline status (absolute increase must be $\geq 10\%$); • Appearance of a new lesion(s), $\geq 50\%$ increase from nadir in SPD^f of > 1 lesion, or $\geq 50\%$ increase in the longest diameter of a previous lesion > 1 cm in short axis; • $\geq 50\%$ increase in circulating plasma cells (minimum of 200 cells/μL) if this is the only measure of disease
Clinical relapse	
 • Clinical relapse requires one or more of the following criteria: 
 • Direct indicators of increasing disease and/or end organ dysfunction (CRAB features) related to the underlying clonal plasma-cell proliferative disorder. It is not used in calculation of time-to-progression or progression-free survival but is listed as something that can be reported optionally or for use in clinical practice; • Development of new soft tissue plasmacytomas or bone lesions (osteoporotic fractures do not constitute progression); • Definite increase in the size of existing plasmacytomas or bone lesions. A definite increase is defined as a 50% (and ≥ 1 cm) increase as measured serially by the SPD^f of the measurable lesion; • Hypercalcemia (> 11 mg/dL); • Decrease in hemoglobin of ≥ 2 g/dL not related to therapy or other non-myeloma-related conditions; • Rise in serum creatinine by 2 mg/dL or more from the start of the therapy and attributable to myeloma; • Hyperviscosity related to serum paraprotein

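### Myeloma-attributed end-organ events without IMWG progression can be missing from both the AE/SAE tables and the efficacy results, and the AE recording rules for them conflict

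*Protocol*

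**What the plan says.** Under the paragraph on lack of efficacy or worsening of disease, Protocol Section 6.1 removes one class of event from the AE form: "Events that are clearly consistent with the expected pattern of progression of the underlying disease". These "will NOT be recorded as AEs. These data will be captured as efficacy assessment data only". The paragraph ends with a safeguard: "If there is any uncertainty as to whether an event is due to disease progression, the event should be reported as an AE".

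Appendix E then lists what is not enough to establish PD. The list includes, among similar findings, "Clinical relapse based on indicators that are not part of the IMWG criteria for PD (e.g., decrease in hemoglobin, hypercalcemia, increase in serum creatinine, hyperviscosity". It adds that clinical relapse as defined in Appendix F "cannot be used to determine PD". The clinical relapse row of Appendix F says of these indicators: "It is not used in calculation of time-to-progression or progression-free survival but is listed as something that can be reported optionally".

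Elsewhere the protocol points the other way. The general AE definition in Section 6.1 counts worsening of an existing illness as an AE. It also counts a laboratory abnormality that needs treatment. Appendix E makes clinically significant changes on physical examination AEs, and likewise a clinically significant laboratory value that leads to treatment.

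**The concern.** The exemption rests on a promise that the efficacy data will hold what the AE form leaves out. In myeloma, worsening disease can show itself as end-organ damage, and the four findings named in Appendix E are of that kind. If such a finding is judged clearly due to myeloma but M-protein, light chains, marrow and lesions do not meet the PD criteria, neither side of the database is required to hold the event.

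This matters because safety and tolerability are the primary objective (Section 3.1), there is no control group (Section 4.2), and an open-label investigator makes the attribution. Attribution is not easy here. Section 6.4 says "Pomalidomide could lead to neutropenia, anemia, and thrombocytopenia", and Section 2.1 places anemia among the most common Grade 3 or higher events in the venetoclax myeloma trials. A confident but mistaken attribution to myeloma would remove a drug-related event from the AE tables.

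**Working it through.** This is mainly a check of rules against each other. The inputs are the recording rules in Protocol Section 6.1 and Appendix E, the PD rules in Appendices E and F, the endpoint definitions in SAP Section 4.3.2 and the safety analyses in SAP Sections 7.1 and 7.2.

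**Step 1: AE and SAE tables.** In Section 6.1 an SAE is an AE that meets a seriousness criterion. An event that is not an AE therefore cannot be an SAE, even if it leads to hospitalization. SAP Section 7.1 summarizes treatment-emergent AEs, so an exempted event appears in none of its tables.

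**Step 2: efficacy results.** PFS counts PD or death from any cause; TTP and DOR count PD or death due to myeloma. None has a clinical-relapse component. The Appendix D schedule has no entry for clinical relapse either. Some lesion-based findings in the clinical relapse row can also qualify as PD; the four findings below cannot.

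**Step 3: laboratory safety results.** Hemoglobin, calcium and creatinine are in Table 3 of Appendix E, and hematology and chemistry are safety endpoints (Section 3.4). SAP Section 7.2 grades laboratory values, assesses change from baseline to maximum and final grade, and lists Grade 3–4 values. It has no filter on attribution. Table 3 has no viscosity test.

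For an event judged clearly due to myeloma, without IMWG PD, and with the exemption applied:

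| Finding | AE/SAE tables (SAP 7.1) | PFS, TTP, DOR (SAP 4.3.2) | Laboratory safety (SAP 7.2) |
|---|---|---|---|
| Hemoglobin fall | absent | absent | value present |
| Hypercalcemia | absent | absent | value present |
| Creatinine rise | absent | absent | value present |
| Hyperviscosity | absent | absent | no required test |

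A laboratory value does not carry seriousness, hospitalization, investigator causality or outcome.

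**Step 4: conflict between the recording rules.** Take a subject hospitalized and treated for hypercalcemia that the investigator confidently attributes to myeloma. Under the worsening-of-disease paragraph there is no AE. Under the general definition in the same section, and under the laboratory rule in Appendix E, there is an AE, and hospitalization makes it serious. No text says which rule prevails.

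**Step 5: weight of one subject.** Planned arm sizes are 23 and 27 (Section 7.2 of the protocol). One missing subject changes an arm's incidence by

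- Arm A: 1/23 = 4.3 percentage points
- Arm B: 1/27 = 3.7 percentage points

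The documents give no rate of end-organ events without IMWG PD, so the number of such subjects cannot be calculated.

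**The case against.** The strongest reply is that few events can fall into the gap. To do so, an event must be clearly due to progression and yet occur without IMWG PD. Any doubt sends it to the AE form, and anemia in a subject on pomalidomide is an obvious source of doubt. When progression is suspected from symptoms, Appendix E requires serum and urine electrophoresis, with plasmacytoma evaluation or skeletal survey as indicated. If the subject deteriorates, it asks for every effort to document PD before new therapy. Confirmed PD then enters PFS and TTP, and any death is a PFS event, subject to the censoring rules for missed assessments. Keeping clinical relapse out of TTP and PFS follows the IMWG criteria that the protocol adopts. The case report form is not among the documents and may have a suitable field.

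Most of this stands, and it limits the size of the problem. It does not close the gap. The uncertainty clause does not help where the investigator is confident but wrong. A possible field on an unseen form is not a requirement in the plan. The conflict between the recording rules remains whatever the frequency.

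A reader might go further and infer that these events reach no safety result at all. The documents do not support that: three of the four findings have values analyzed under SAP Section 7.2 regardless of attribution, and treatments given are recorded as concomitant medication with the reason for use.

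A reader might also estimate a count from the non-responders expected at the target response rates: 23 × 0.30 + 27 × 0.40 = 6.9 + 10.8 = 17.7 of 50. Any event rate applied to these 17.7 would be an assumption, and the calculation would not exclude subjects with IMWG PD, who are already in the efficacy results.

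**Conclusion.** The point holds in a limited form. For an event confidently attributed to myeloma, without IMWG PD, the plan can lose the clinical record (seriousness, hospitalization, causality and outcome) from both the AE/SAE tables and the efficacy results. For hyperviscosity not even a laboratory value is required. Separately, the exemption contradicts the general AE definition and two rules in Appendix E, so recording may differ between sites.

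The frequency is unknown and probably low, but at these arm sizes each subject is visible in an incidence table. The conclusion assumes that sites apply the exemption as written and that the case report form has no mandatory field for such events. ORR, its tests and the sample size are not affected. The change is worth making because safety is the primary objective and the cost is low.

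**What to change.** Reconcile the worsening-of-disease paragraph in Section 6.1 with the general AE definition there and with the physical examination and laboratory rules in Appendix E:

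- Limit the exemption to the finding of IMWG PD itself, that is, the M-protein, light-chain, marrow or lesion change scored under Appendix F.
- Record end-organ and symptomatic events attributed to myeloma on the AE form, with a flag for disease under study.
- In SAP Section 7.1, tabulate AEs with and without the flagged events.

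Any exemption from expedited reporting may stay as it is, and clinical relapse can remain outside PD, PFS and TTP. The cost is some extra AE entries, one flag and one extra table. Reported AE rates will be slightly higher, and the table without flagged events lets a reader see by how much.

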6.2 Recording Data and Analyses of Safety Findings

AEs will be coded using the Medical Dictionary for Regulatory Activities. Details on the statistical analyses for safety will be provided in the SAP.

6.3 Reporting Adverse Events and Intercurrent Illnesses

In the event of an SAE, whether associated with study drug or not, the investigator will notify clinical pharmacovigilance within 24 hours of the site being made aware of the SAE by entering the SAE data into the electronic data capture system. SAEs that occur before the site has access to the RAVE® system, or if RAVE is not operable, should be documented on the SAE nonCRF forms and emailed (preferred route) or faxed to clinical pharmacovigilance within 24 hours of the site being made aware of the SAE (refer to [Appendix L](#) for safety reporting contact information).

6.4 Toxicity Management

Venetoclax: Venetoclax could lead to suppression of lymphocytes. In addition, clinically significant neutropenia may also be observed. Both lymphopenia and neutropenia could increase the risk for infections, including opportunistic infections. Venetoclax treatment can also lead to TLS. Subjects will be managed based on their TLS risk factors as detailed below.

Pomalidomide: Pomalidomide could lead to neutropenia, anemia, and thrombocytopenia. Among the nonhematologic toxicities, venous and arterial thromboembolism, hepatotoxicity, hypersensitivity reactions, dizziness and confusional state, and neuropathy have been reported with pomalidomide.

Dexamethasone: Dose modifications or discontinuation may be necessary for gastrointestinal events, acute pancreatitis, neurologic disorders or muscle weakness, and edema or hyperglycemia.

Subjects will be monitored for these events throughout the study and treatment may be discontinued or adjusted as appropriate. Dose modifications and treatment guidelines for drug-related toxicities (venetoclax, pomalidomide, or dexamethasone) are provided in [Appendix I](#). If an investigator considers it necessary, subjects who interrupt study therapy for longer than 28 days may be discontinued from further study therapy.

Prophylaxis and Management of Tumor Lysis Syndrome

Venetoclax and pomalidomide can cause rapid reduction in tumor and thus poses a risk for TLS. Changes in electrolytes consistent with TLS that require prompt management can occur as early as 6 to 8 hours following the first dose of venetoclax ([Appendix H](#)). Definitions of laboratory TLS and clinical TLS are provided in the [Appendix G](#) (Howard grading classification).

There is a potential for TLS in subjects affected by hematologic malignancies. Depending on the specific tumor type, risk factors may include one or more of the following: bulky disease or high tumor burden, elevated pretreatment lactate dehydrogenase levels, elevated leukocyte count, renal insufficiency, and dehydration.

MM subjects with high tumor burden (e.g., high bone marrow plasma cell infiltration, plasma cell leukemia, or bulky plasmacytomas), rapidly increasing M-protein or light chains or high proliferative activity, plasmablastic morphology, or compromised renal function (CrCL < 50 mL/minute) may be at higher risk of developing TLS.¹¹ Additionally, subjects with t(11;14) and high bone marrow plasma cell infiltration or a significant number of circulating plasma cells appear to have an increased risk for TLS when treated with venetoclax.

Consider TLS prophylaxis with oral hydration (at least 1 to 2 L, as tolerable) in all subjects at least 72 hours before the first day of dosing with venetoclax and pomalidomide. Prophylaxis with uric acid reducing agents may be required for subjects with high uric acid levels. Monitor for clinical and laboratory evidence of TLS during treatment ([Appendix G](#)) and manage abnormalities in serum creatinine, uric acid, and electrolytes promptly according to institutional guidelines (guidance also available in [Appendix H](#)).

For subjects with t(11;14) and > 50% bone marrow plasma cell infiltration or CrCL < 50 mL/minute, oral hydration as aforementioned is required and chemistry laboratory tests (phosphate, potassium, calcium, uric acid, creatinine, lactate dehydrogenase, and AST at a minimum) should be done at approximately 6 hours after the first dose with venetoclax. Consider uric acid-lowering drugs in subjects at higher risk for TLS. More intensive measures (e.g., IV hydration, frequent monitoring of laboratory values, hospitalization, etc.) should be considered at the investigator's discretion or in accordance with institutional guidelines. All TLS prophylaxis measures should be appropriately recorded in the eCRF.

In case of evidence of TLS, dosing with venetoclax should be interrupted. Drug interruption for up to 72 hours following transient (i.e., lasting < 48 hours) chemical changes and laboratory TLS will not require a dose reduction. If the TLS has not resolved within 72 hours, then a dose reduction should be considered. The subject may be allowed to re-escalate to the final dose based on a risk assessment (including tumor burden status). If active correction of electrolytes was performed, the first dose of

venetoclax should only be given when electrolytes have been stable without additional treatment for at least 24 hours.

If a subject meets criteria for clinically significant laboratory or clinical TLS, the subject must dose reduce (refer to the [Appendix I](#), as applicable). The subject may be allowed to re-escalate to the intended cohort dose based on a risk assessment (including tumor burden status) after discussion between the investigator and the TA MD.

Additional TLS prophylaxis and monitoring (more frequent laboratory sample collection, IV hydration, dose ramp-up requirements, etc.) can be implemented as needed based upon review of safety data (e.g., if a higher than expected rate of laboratory TLS is observed or cases of clinical TLS are identified).

Management of Neutropenia and Other Cytopenias

Venetoclax and pomalidomide can cause cytopenias including clinically significant neutropenia and lymphopenia that can increase risk for serious infection including opportunistic infections. Subjects with a history of neutropenia who have received multiple prior therapies and/or have significant bone marrow involvement may be at a particularly high risk. Grade 3 or 4 neutropenia has been reported in subjects treated with venetoclax and pomalidomide.

Complete blood counts should be monitored throughout the treatment period. Anti-infective prophylaxis and granulocyte-colony stimulating factor (G-CSF) for management of neutropenia should be considered per institutional guidelines. Subjects should receive anti-infective prophylaxis (e.g., amoxicillin/clavulanic acid or levofloxacin or equivalent per institutional guidelines) when Grade 4 neutropenia develops (ANC < 500 cells/ μ L) and continued until the neutropenia improves to Grade 3 or better (ANC > 500 cells/ μ L). Please refer to the [Appendix I](#) for guidance on dose reductions or interruptions related to venetoclax or pomalidomide toxicities.

Management of Decrease in Spermatogenesis

Venetoclax may cause a decrease in spermatogenesis. Male subjects considering preservation of fertility should bank sperm before initiating treatment with venetoclax.

Embryo-Fetal Toxicity

Pomalidomide is contraindicated in pregnancy. Pomalidomide is a thalidomide analog; thalidomide is a known human teratogen that causes severe life-threatening birth defects. Refer to the pomalidomide package insert for details.¹⁰

Venous and Arterial Thromboembolism

Deep venous thrombosis, pulmonary embolism, myocardial infarction, and stroke occur in subjects with multiple myeloma treated with pomalidomide. Antithrombotic prophylaxis is recommended for subjects with a history of cardiovascular disease or per investigator discretion. Refer to the pomalidomide package insert for details.¹⁰

Management of Infection

Subjects should receive anti-infective prophylaxis (e.g., amoxicillin/clavulanic acid or levofloxacin or equivalent per institutional guidelines) at least during the first 90 days of study and upon disease

progression for at least 30 days unless contraindicated per investigator discretion. Furthermore, subjects deemed at high risk of infection should receive immunoglobulin replacement therapy (i.e., IVIG) per institutional guidelines or at the investigator's discretion.

The use of antibiotics that are moderate or strong CYP3A inhibitors should be avoided or used with caution and with appropriate venetoclax dose modification (refer to [Appendix I](#)) as per protocol.

All subjects receiving venetoclax should be closely monitored for infections and in the event of a Grade ≥ 3 or serious infection, treatment with venetoclax should be interrupted and upon resolution, treatment can be either resumed at a reduced dose or discontinued, depending on investigator's clinical judgment.

Please refer to [Table 9](#) and [Table 10](#) for guidance on dose interruptions and/or reductions related to venetoclax toxicities.

Potential for drug-drug interactions should be considered. Please refer to [Appendix J](#) for a description of prohibited and cautionary medications.

Management of Other Toxicities

If other events occur that are related to venetoclax or pomalidomide, the investigator may interrupt or dose reduce venetoclax and/or pomalidomide, as appropriate (refer to [Appendix I](#)).

Pomalidomide must be permanently discontinued for angioedema, skin exfoliation, bullae, or any other severe dermatologic reaction.

All subjects should be monitored for new onset hematologic, hepatic, and renal toxicities with dose delay or reduction as appropriate. Please follow local, approved product label or applicable summary of product characteristics¹² for monitoring guidelines for pomalidomide or [Appendix I](#) for venetoclax.

Dexamethasone dose modifications or discontinuation may be necessary for Grades 1 to 2 gastrointestinal disorders that do not respond to appropriate treatment, > Grade 3 gastrointestinal events, acute pancreatitis, > Grade 2 neurologic disorders or muscle weakness, and \geq Grade 3 edema or hyperglycemia (refer to [Appendix I](#)).

